11.5. Multiple Sclerosis Functional Composite

The MSFC ([Cutter 1999](#)) is a battery of the following 3 individual scales:

- The Timed 25-Foot Walk is a quantitative measure of lower extremity function
- The 9-Hole Peg Test is a quantitative measure of upper extremity (arm and hand) function
- The Symbol Digit Modalities Test (SDMT) is a measure of executive function cognition that assesses processing speed, flexibility, and calculation ability ([Drake 2010](#)).

The same person, either the evaluator or another independent designated team member trained in conducting MSFC assessments should administer the 3 scales that make up the MSFC with each participating patient throughout the trial. The MSFC z-score is calculated by creating z-scores for each component of the MSFC, as explained below, and averaging them to create an overall composite score, ie, $MSFC\ z\text{-score} = (Z_{25\text{-foot-walk}} + Z_{9HPT} + Z_{SDMT})/3$, where Z_{xxx} refers to Z-scores.

Details on the calculations of the z-score for each component will be described in the statistical analysis plan (SAP).

11.6. Low-Contrast Letter Acuity Test

The LCLA which is performed with the MSFC assessments, is performed with a standardized set of charts (Sloan letter charts or Tumbling E charts) to assess low contrast visual acuity. Each chart corresponds to a different contrast level, and charts are scored according to the number of letters that are identified correctly. The LCLA captures aspects of neurological dysfunction that

is not assessed by the EDSS or MSFC, and has been proposed as an additional component to the MSFC (Balcer 2003).

11.7. Multiple Sclerosis Quality of Life-54

The Multiple Sclerosis Quality of Life-54 (MSQOL-54) is a multidimensional health-related quality of life measure that combines both generic and MS-specific items into a single instrument (Vickrey 1995). This 54-item instrument generates 12 subscales along with two summary scores, and two additional single-item measures. The subscales are: physical function, role limitations-physical, role limitations-emotional, pain, emotional well-being, energy, health perceptions, social function, cognitive function, health distress, overall quality of life, and sexual function. The summary scores are the physical health composite summary and the mental health composite summary. The single item measures are satisfaction with sexual function and change in health.

The MSQOL-54 is a structured, self-report questionnaire that the patient can generally complete with little or no assistance. It may also be administered by an interviewer. However, patients with visual or upper extremity impairments may need to have the MSQOL-54 administered as an interview by the trial nurse (or trial coordinator). Interviewers should be trained in basic interviewing skills and in the use of this instrument.

12. SAFETY ASSESSMENTS

12.1. Clinical Safety Assessments

12.1.1. Physical Examination

A complete physical examination will include evaluation of heart, lung, head and neck, abdominal, skin, and extremities. The EDSS, performed by the evaluator, serves as the neurological examination. An interim (or brief) physical examination will include areas with previously noted abnormalities and/or that are associated with any new complaints from the patient.

Initial neurological examination will be a part of the physical examination at baseline and if warranted, will be performed at an unscheduled visit. All significant findings that are present at baseline must be reported on the relevant current medical conditions eCRF. Significant findings made after enrollment that meet the definition of an AE must be recorded on the AE eCRF.

12.1.2. Vital Signs

Blood pressure, heart rate, and body temperature will be assessed. Systolic and diastolic blood pressure and heart rate will be assessed in a sitting position using an automated validated device, if available. In case the cuff sizes available are not large enough for the patient's arm circumference, a sphygmomanometer with an appropriately sized cuff may be used.

Patients who require RPC1063 dose escalation will be carefully monitored after the first dose of investigational drug with a 6-hour post-dose monitoring period of hourly recording of heart rate and blood pressure as described in Section [12.1.11](#).

Guidelines regarding monitoring of patients with an AE of bradycardia are also described in Section [12.1.11](#).

12.1.3. Electrocardiogram

A 12-lead ECG is to be performed after the patient has been resting quietly for at least 5 minutes.

The 12-lead digital ECG devices will be provided to each clinical site by the central ECG laboratory for the duration of the trial. Detailed instructions describing the process for recording and transmission of the digital ECGs will be outlined in the trial-specific manual and provided to the site before the start of the trial. A 12-lead ECG will be performed before and 6 hours after the first dose of investigational drug administration, while the patient is at the clinic. The 6-hour post-dose ECG will be evaluated by the treating physician, with input from a local cardiologist or a central reader, if needed, to confirm if extended monitoring is required. Baseline or pre-dose ECG should be available for comparison to the post-dose ECG in order to determine if discharge criteria are met. Additional ECG monitoring will be performed on Days 5 and 8 if cardiac issues are identified on the prior day of dose escalation, as described in Section [12.1.11](#).

Only clinically significant ECG abnormalities should be reported in the AE eCRF. Clinically significant findings on the baseline ECG must be discussed with the Medical Monitor before enrolling the patient in the trial.

12.1.4. Pulmonary Function Tests

Pulmonary function tests (PFTs) including FEV₁ and FVC measurements will be performed as scheduled in [Table 2](#). In addition, DLCO will be assessed (where locally available). DLCO will only be assessed at the End of Treatment/Early Termination Visit. DLCO will not be required at sites where there is no local testing facility.

These tests will be performed at a high quality pulmonary function laboratory or respiratory department. Please refer to the American Thoracic Society/European Respiratory Society guidelines for standardization of spirometry and single breath determination of carbon monoxide uptake in the lung ([MacIntyre 2005](#); [Miller 2005a](#); [Miller 2005b](#)).

For patients with abnormal PFTs (based on predicted FVC or FEV₁ < 70%), PFTs will be repeated within < 30 days. Upon confirmation of abnormal PFTs, patients will be followed until resolution or no further improvement is expected by the Investigator (based on a follow-up period of not less than 3 months). If the PFT decrease persists, consult with the Medical Monitor. If patients have a confirmed decline in PFT values (FEV₁ and/or FVC) < 50% of the predicted values, investigational drug should be discontinued and the Investigator should consult the Medical Monitor.

If a patient is temporarily or permanently discontinued from investigational drug due to a respiratory AE, the Investigator should ensure that the patient has adequate evaluations as clinically indicated.

12.1.5. Ophthalmological Examination

OCT will be performed as scheduled in [Table 2](#).

Suspicion of Macular Edema. If abnormal OCT findings, or visual signs or symptoms of macular edema are observed, a general ophthalmologic examination including eye history, visual acuity, and dilated ophthalmoscopy will also be performed. If the ophthalmic evaluation reveals abnormalities suggestive of macular edema, investigational drug will be temporarily discontinued. Patients will be followed with repeat ophthalmology examinations until evaluations return to baseline or no further improvement is expected (based on a follow-up period of not less than 3 months).

Confirmed Macular Edema. Investigational drug must be permanently discontinued in any patient with a confirmed diagnosis of macular edema that is of new onset or worsened since baseline. Patients with a confirmed diagnosis of macular edema must be evaluated by an ophthalmologist on a monthly basis or more frequently if needed based on the ophthalmologist's judgment. Further ophthalmological evaluations will be conducted until resolution or no further improvement is expected by the ophthalmologist (based on a follow-up period of not less than 3 months). If the patient does not show definite signs of improvement on examination 6 to 8 weeks after discontinuation of investigational drug, then therapy for macular edema should be initiated in conjunction with an ophthalmologist experienced in the management of this condition.

12.1.6. Dermatological Examination

Dermatological (skin) evaluations will be performed by the treating Investigator or designee as part of the physical examination at baseline, and as scheduled in [Table 2](#). Patients with any abnormal finding noted during the examination will be referred to an appropriately qualified dermatologist for evaluation and treatment, if warranted.

12.1.7. Suicidality Assessment

Suicidality will be assessed using the C-SSRS ([Posner 2011](#)) as indicated in [Table 2](#). The C-SSRS is a rater-administered questionnaire. A patient indicating suicidal ideation on the C-SSRS will be assessed by the Investigator and referred for further assessment by other health care professionals as indicated. It is important that the C-SSRS be completed early in the visit to ensure the report and any associated alerts are reviewed during the visit, while the patient is at the site.

12.1.8. Dependence and Withdrawal Battery

The Dependence and Withdrawal Battery include the C-SSRS and additional assessments:

12.1.8.1. Physician's Withdrawal Checklist (PWC-20)

The PWC-20 is a rater-administered 20-item scale to assess signs and symptoms of withdrawal. Twenty items are rated on a 4-point scale as not present (0 points), mild (1 point), moderate (2 points), or severe (3 points). The points from all items are calculated as a total score. Higher scores indicate more severe withdrawal symptoms ([Rickels 2008](#)).

12.1.8.2. Hospital Anxiety and Depression Scale (HADS)

The HADS is a validated patient reported outcome for assessing anxiety and depression ([Zigmond 1983](#); [Bjelland 2002](#)). It consists of 14 items in total, 7 items related to anxiety and 7 items related to depression. For each item patients select a statement (valued at 0 to 3 points) that closest matches their own feeling over the past week. Separate total scores for anxiety and depression are derived by adding up points. Total scores can range from 0 to 21 points. Higher scores indicate more severe anxiety and depression and scores of 8 to 10 are generally considered indicative of borderline anxiety/depression disorders and scores of 11 and higher are generally considered indicative of anxiety/depression disorders.

12.1.8.3. Epworth Sleepiness Scale (ESS)

The ESS is a validated self-administered questionnaire with 8 questions ([Johns 1997](#)). Respondents rate on a 4-point scale (0 to 3) their chances of dozing off or falling asleep while engaged in 8 different activities. The ESS score is the sum of 8 item scores and can range from 0 to 24 points. Higher scores indicate more daytime sleepiness.

12.1.9. Monitoring of Adverse Events and Serious Adverse Events

Throughout the course of the trial, every effort must be made to remain alert to possible AEs or SAEs. Refer to [Section 12.3](#) for definitions of AEs/SAEs, monitoring, and reporting. Refer to

Section 12.4.2 for AESIs and Section 12.4.3 for monitoring of patients with AEs, SAEs, and AESIs.

Reductions in ALC levels for patients in this study is an expected primary pharmacodynamic effect. Reductions in ALC, in general, need not be reported as AEs unless there are clinical consequences. The protocol requirements in Section 12.2.1 should be followed for confirmed ALC < 200 cells/ μ L. The decision to report decreased ALC as an AE is at the Investigator's discretion.

12.1.10. Monitoring of Concomitant Therapy

The use of concomitant medication and procedures will be monitored throughout the trial. Refer to Section 9.5 for prohibited concomitant therapies.

12.1.11. Guidelines for Monitoring Patients Taking Their Day 1 Dose of RPC1063

On Day 1 of treatment, careful cardiac monitoring is required for patients undergoing RPC1063 dose escalation. The Investigator is responsible for monitoring the patient following the first intake of the investigational drug. The Investigator must review the pre-dose and post-dose ECG, and heart rate and blood pressure during the 6-hour monitoring period, and assess discharge status at 6 hours after dosing.

Resting heart rate and blood pressure in the sitting position will be measured before the first dose of investigational drug, then every hour (\pm 10 min) for at least 6 hours thereafter (by the Investigator, an assisting nurse, or other medically qualified staff member). When obtaining the heart rate and blood pressure before the first dose, the patient should be allowed to rest in a seated position at least 5 minutes before taking measurements. The heart rate and sitting blood pressure measurements should be repeated 2 additional times (only before the first dose of investigational drug) and all of these measurements should be recorded in the eCRF. The repeat measurements will be made at approximately 2-minute intervals. For the hourly measurements after investigational drug administration, heart rate and sitting blood pressure will be measured once and recorded in the eCRF. The lowest pre-dose value of sitting heart rate and blood pressure (based on systolic blood pressure) will be recorded in the case report form and serve as baseline for comparison to post-dose values.

Patients should receive the first dose of investigational drug before 12:00 pm (noon) in the clinic. The first dose of RPC1063 should be administered in a setting in which resources to appropriately manage symptomatic bradycardia are available. A member of the Investigator team should be available to monitor the patient for the 6-hour monitoring period and will need to report any abnormalities to the Investigator. Atropine and isoproterenol or epinephrine need to be readily available to the site personnel. Although atropine and isoproterenol are preferred, epinephrine may be used as a substitute if the preferred medications are not available.

If any of the following criteria are met, additional extended monitoring should be instituted until the finding has resolved. Baseline and hourly vital signs measurements (Hours 1 through 6) should be used to assess heart rate (criteria 1 and 2 below) and ECG should be used to assess for atrioventricular (AV) block and Fridericia's corrected QT (QTcF) interval (criteria 3 and 4 below).

1. The heart rate 6 hours post-dose is < 45 bpm, and > 10 bpm below predose
2. The heart rate 6 hours post-dose is at the lowest value post-dose (suggesting that the maximum PD effect on the heart may not have occurred)
3. The ECG 6 hours post-dose shows new onset second degree or higher AV block
4. The ECG 6 hours post-dose shows a prolonged QTcF interval (> 450 msec men, > 470 msec women).

Should post-dose symptomatic bradycardia occur, the treating physician should be notified and he or she should initiate appropriate management, begin continuous ECG monitoring, and continue observation until the symptoms have resolved.

Should a patient require pharmacologic intervention for symptomatic bradycardia, continuous overnight ECG monitoring in a medical facility should be instituted, and the first dose monitoring strategy should be repeated the following day (Day 2). The first dose monitoring strategy should also be repeated at Day 5 or at Day 8 if any cardiac safety issues were observed on the previous day of dose escalation.

Patients should have written instruction on when to return to clinic and a 24-hour contact phone number to call in the event of any new or warranted symptoms (eg, chest pain, dizziness, palpitations, syncope).

12.2. Laboratory Assessments

The central laboratory will analyze the laboratory samples. Further details of the procedures to be followed for sample collection, storage, and shipment will be documented in a laboratory manual.

Additional and repeat laboratory safety testing, preferably using the central laboratory, may be performed at the discretion of the Investigator. The following laboratory tests will be performed to assess the safety profile of RPC1063:

- Hematology - Red blood cell count, total and differential white blood cell (WBC) count (basophils, eosinophils, lymphocytes, monocytes, and neutrophils), platelet count, hemoglobin, hematocrit, mean corpuscular volume, mean corpuscular hemoglobin, and mean corpuscular hemoglobin concentration.
- Chemistry
 - Full chemistry panel at Baseline, every 12 months (annually), at the 28-Day Safety Follow-up Visit, and at End of Treatment/Early Termination Visit: sodium, potassium, chloride, calcium, magnesium, phosphate, blood urea nitrogen, glucose, albumin, alkaline phosphatase, creatinine, serum glutamic pyruvic transaminase (SGPT)/alanine aminotransferase (ALT), serum glutamic oxaloacetic transaminase (SGOT)/aspartate aminotransferase (AST), gamma-glutamyl-transferase (GGT), amylase, total bilirubin, conjugated bilirubin, total cholesterol, triglycerides, high-density lipoprotein (HDL), and low-density lipoprotein (LDL).

- All other visits: blood urea nitrogen, albumin, alkaline phosphatase, creatinine, SGPT/ALT, SGOT/AST, GGT, amylase, total bilirubin, conjugated bilirubin.
- Urinalysis at Baseline, at the 28-Day Safety Follow-up Visit, and at End of Treatment/Early Termination Visit - leukocytes, specific gravity, bilirubin, blood, glucose, ketones, pH, protein, and urobilinogen.
- Exploratory measurements of immune response (eg, anti-SARS-CoV-2 serology) will be assessed from blood samples collected at trial visits and end of treatment, and the potential association between these measurements and selected endpoints related to safety and/or efficacy.
- Pregnancy test - In women of childbearing potential, urine beta-human chorionic gonadotropin (hCG) test will be performed at Baseline if more than 1 month has elapsed from the last pregnancy test in the parent trial. Urine beta-hCG test will be performed in women of childbearing potential at each scheduled visit. Between scheduled visits, up until the 90-Day Safety Follow-up Visit, monthly home urine pregnancy tests should be performed by the patient. If a urine pregnancy test result is positive, the Investigator will instruct the patient to suspend further RPC1063 dosing, if applicable, and schedule a follow up appointment as soon as possible. A serum pregnancy test will be performed for confirmation, including after the 90-Day Safety Follow-up visit, if needed.

12.2.1. Clinical Laboratory Parameters and Abnormal Laboratory Test Results

Hematology

Starting with the Month 3 visit (ie, excluding the Baseline visit), complete hematology laboratory values will be available to the Investigator. Reductions in ALC levels is a known pharmacodynamic effect of RPC1063. If any of the following results are observed, the Investigator will be notified and asked to repeat the laboratory tests within approximately 7 days:

- Absolute lymphocyte count [ALC] < 200 cells/ μ L
- Absolute neutrophil count [ANC] < 1000 cells/ μ L
- Total WBC > 20,000 cells/ μ L

If the ANC is confirmed < 1000 cells/ μ L, the Investigator will be requested to closely monitor for risk of serious infection and institute appropriate follow-up at his or her discretion.

If ALC is confirmed < 200 cells/ μ L, the Investigator will temporarily discontinue treatment and then consult the Medical Monitor. Laboratory testing will be repeated weekly until ALC is > 500 cells/ μ L. When ALC has returned to > 500 cells/ μ L, treatment may be reinitiated at the Investigator's discretion. (See Section 9.3.1 for instructions on resuming treatment after missing doses.)

For patients who permanently discontinue treatment or complete the trial, central laboratory testing of ALC will continue every 14 days (\pm 3 days) after discontinuation of RPC1063 or the End of Treatment/Early Termination Visit until ALC is above the lower limit of normal.

If an ALC Follow-up Visit is needed within the window of the 90-Day Safety Follow-up Visit, the patient should only return for the 90-Day Safety Follow-up Visit and ALC should be collected at that visit.

If the patient has started a lymphocyte-depleting treatment during the Safety Follow-up period, ALC should only be determined at the 90-Day Safety Follow-up Visit. The Medical Monitor should be consulted if the ALC is not $>$ LLN by the Day 90 Safety Follow-up Visit for subjects not started on lymphocyte-depleting disease modifying therapies (DMTs), and ALC visits should continue every 14 days (\pm 3 days) until the Investigator is notified to discontinue.

Liver Function Tests

If patients have elevations in ALT and/or AST $>$ 3x the upper limit of normal (ULN), a retest should be performed as soon as possible but not later than 14 days after the original test. If the abnormality is confirmed, weekly testing should continue until ALT and AST are $<$ 3x ULN. If the ALT and/or AST stabilizes at a level $>$ 3x ULN, the Medical Monitor may agree to less frequent testing. The Investigator should establish causality. In addition, the confirmed elevation $>$ 3x ULN is an AESI (see Section 12.4.2) and should be reported by the Investigator.

At any time, if any of the following occur and there are no apparent alternative causes for the finding, the investigational drug must be permanently discontinued:

- ALT or AST $>$ 8x ULN or
- ALT or AST $>$ 5x ULN with confirmation, within 2 weeks or
- ALT or AST $>$ 3x ULN and (total bilirubin $>$ 2x ULN or INR $>$ 1.5) or
- ALT or AST $>$ 3x ULN with the appearance of fatigue, nausea, vomiting, right upper quadrant pain or tenderness, fever, rash, and/or eosinophilia ($>$ 5%).

The Investigator should establish causality.

After discontinuation due to elevation of ALT or AST $>$ 5x ULN or concurrent elevations of ALT or AST $>$ 3x ULN and bilirubin $>$ 2x ULN, further liver function evaluation should be performed (for example, coagulation panel and alkaline phosphatase) in consultation with the Medical Monitor.

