- ^b The Unscheduled Relapse Visit will be conducted if a possible relapse is suspected at any time prior to the 90-Day Safety Follow-up Visit. The visit is to be planned as soon as possible, ideally within 7 days of symptom onset. If the relapse is confirmed, the Unscheduled Relapse Visit and Early Term procedures may occur at the same visit. If the relapse is not confirmed, patients should return to their usual visit schedule.
- ^c Central laboratory testing of ALC will continue every 14 days (\pm 3 days) after discontinuation of RPC1063 or the End of Treatment/Early Termination Visit until ALC is above the lower limit of normal for patients who discontinue treatment. If an ALC Follow-up Visit is needed within the window of the 90-Day Safety Follow-up Visit, the patient should only return for the 90-Day Safety Follow-up Visit and ALC should be collected at that visit. If a patient has started a lymphocyte-depleting treatment during the safety follow up period, ALC should only be determined at the 90-Day Safety Follow-up Visit. The Medical Monitor should be consulted if the ALC is not $>$ LLN by the Day 90 Safety Follow-up Visit for subjects without lymphocyte depleting DMTs and ALC visits should continue every 14 days (\pm 3 days) until the Investigator is notified to discontinue.
- ^d Baseline (Day 1), 28-Day Safety Follow-up Visit, End of Treatment/Early Termination clinical laboratory tests include chemistry (full panel), hematology, and urinalysis. Every 3/6 months clinical laboratory tests include: Chemistry (abbreviated panel) and hematology. Every 12 months (annually) clinical laboratory tests include: Chemistry (full panel) and hematology.
- ^e Urine beta-human chorionic gonadotropin (hCG) test at each visit for women of childbearing potential only. Between scheduled visits up until the 90-Day Safety Follow-up Visit, monthly home urine pregnancy tests should be performed by the patient. If a urine pregnancy test result is positive, the Investigator will instruct the patient to suspend further RPC1063 dosing, if applicable, and schedule a follow-up appointment as soon as possible. A serum pregnancy test will be performed for confirmation, including after the 90-Day Safety Follow-up Visit, if needed.

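### The INR arm of the hepatic stopping rule has no scheduled or triggered INR measurement behind it

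*Combined protocol and SAP*

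**What the plan says.** Under Liver Function Tests, Section 12.2.1 lists four findings after which, if no other cause is apparent, "the investigational drug must be permanently discontinued". The third is "ALT or AST $>$ 3x ULN and (total bilirubin $>$ 2x ULN or INR $>$ 1.5". The others are ALT or AST above 8x ULN, above 5x ULN with confirmation within two weeks, and above 3x ULN with any of a list of symptoms or eosinophils above 5%.

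When ALT or AST first exceeds 3x ULN, "a retest should be performed as soon as possible but not later than 14 days after the original test". A confirmed elevation leads to weekly testing until both fall below 3x ULN. If values settle above that level, "the Medical Monitor may agree to less frequent testing".

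Section 12.2 sets out the safety laboratory panels. The abbreviated chemistry panel reads: "All other visits: blood urea nitrogen, albumin, alkaline phosphatase, creatinine, SGPT/ALT, SGOT/AST, GGT, amylase, total bilirubin, conjugated bilirubin". Table 2, footnote d, assigns panels to visits: "Every 3/6 months clinical laboratory tests include: Chemistry (abbreviated panel) and hematology". Annual visits have full chemistry and hematology. Beyond the scheduled panels, "Additional and repeat laboratory safety testing, preferably using the central laboratory, may be performed at the discretion of the Investigator".

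Coagulation testing is mentioned once, for patients already taken off drug for ALT or AST above 5x ULN, or above 3x ULN with bilirubin above 2x ULN: "further liver function evaluation should be performed (for example, coagulation panel and alkaline phosphatase) in consultation with the Medical Monitor".

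**The concern.** A mandatory stopping rule works only if someone is obliged to measure its inputs. Here one input, INR, is left to the individual investigator or Medical Monitor, at about 275 sites (Section 7.1). A patient can meet a criterion for permanent discontinuation while the site, in full compliance with the protocol, sees no criterion met and continues dosing.

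The provision for relaxing weekly testing adds to this. A patient whose transaminases plateau above 3x ULN can move to less frequent monitoring without an INR ever having been drawn.

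Long-term safety and tolerability is the primary objective (Section 6.1), and a confirmed transaminase elevation above 3x ULN is an adverse event of special interest (Section 12.4.2). The issue is patient protection and uniform application of the rule. No endpoint or planned analysis is affected.

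**Working it through.** The plan states no figure to reproduce. The check sets each laboratory input to the stopping rule against every place where the protocol requires a test.

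**Step 1: tests listed in Section 12.2.** Hematology 13 (red cells, total white cells, five differential counts, platelets, hemoglobin, hematocrit, three red-cell indices); full chemistry 21, which contains all 10 abbreviated-panel tests; urinalysis 9. Total 13 + 21 + 9 = 43. INR, PT or any other coagulation test: 0 of 43. The remaining items in Section 12.2 are exploratory immune-response and pregnancy tests.

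**Step 2: inputs to the stopping rule.**

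| Input | Routine 3/6-month and annual draws | Named in triggered testing above 3x ULN |
|---|---|---|
| ALT | Yes, both chemistry panels | Yes |
| AST | Yes, both chemistry panels | Yes |
| Total bilirubin | Yes, both chemistry panels | No |
| Eosinophils | Yes, hematology differential | No |
| INR | No | No |

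Four of five inputs are on every routine draw. Bilirubin and eosinophils are not named for the retest either, but they come from the same scheduled visit that reveals the transaminase elevation. INR has no source at any point.

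**Step 3: other mentions.** Table 1 defines INR, PT and PTT, but no test list uses them. The coagulation panel in Section 12.2.1 is an example test, applies after the drug has been stopped, and follows stops on other criteria. It cannot supply the INR needed to decide whether to stop.

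**Step 4: worked case.** Take ALT 4x ULN, total bilirubin 1.8x ULN, INR 1.8, no listed symptoms, eosinophils at or below 5%, and no apparent alternative cause.

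- ALT above 8x: 4 is not above 8. Not met.
- ALT above 5x, confirmed: 4 is not above 5. Not met.
- ALT above 3x with bilirubin above 2x: 4 exceeds 3, but 1.8 is not above 2. Not met.
- ALT above 3x with INR above 1.5: 4 exceeds 3 and 1.8 exceeds 1.5. **Met.**
- ALT above 3x with symptoms or eosinophilia: not met.

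The only criterion met is the one whose second input is never required.

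**Step 5: work-up after stopping.** The work-up sentence covers stops above 5x ULN (and so those above 8x) and stops above 3x with raised bilirubin. It omits stops on the INR arm and on the symptom/eosinophilia criterion. This is a secondary point, and the main finding does not depend on it.

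**The case against.** The strongest counter-argument is that INR matters only once ALT or AST exceeds 3x ULN, so its absence from routine panels is no fault, and by then the patient is already under close review. Section 12.2.1 calls for weekly testing and a causality assessment and makes the confirmed event a reportable one of special interest. Section 12.4.4 requires follow-up, the DMC reviews safety data (Section 12.5), and the investigator may order an INR or withdraw the patient (Sections 12.2 and 8.2). It is right that INR need not be on routine draws, and the proposed change does not put it there. But none of these safeguards requires an INR, so they make detection more likely without assuring it.

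The affected group is also small: a patient must escape every other criterion and still have a raised INR. This stands. It limits the weight of the point, but the rule as written still lacks an input.

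The laboratory manual and the safety management plan (Section 12.4) are not among the documents and might ask for INR. This cannot be excluded, although Section 12.2 describes the manual as covering sample collection, storage and shipment.

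On the work-up sentence, withdrawn patients should already have full chemistry, including alkaline phosphatase, at the End of Treatment and Day 28 visits, and a stop on the INR arm already has an INR result. That reduces the secondary point largely to wording.

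Finally, an amendment needs ethics approval (Section 16.1), and little of the trial remains. Both are true and are counted in the cost below.

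**Conclusion.** The concern holds. The protocol makes ALT or AST above 3x ULN with INR above 1.5 a mandatory reason to stop, and neither the schedule nor the triggered testing requires an INR. It is the only one of the rule's five laboratory inputs without a required measurement.

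The exposed group is narrow: transaminases above 3x ULN but neither above 8x nor confirmed above 5x, bilirubin at or below 2x ULN, none of the listed symptoms, eosinophils at or below 5%, INR above 1.5, and no apparent alternative cause. The documents give no rate for it, so no number of patients can be stated.

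The conclusion assumes that neither the laboratory manual nor the safety management plan already requires an INR. The change should be made on patient-safety grounds; it does not bear on the validity of the analyses.

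**What to change.** In Section 12.2.1, name ALT, AST, total bilirubin and INR as the tests on the retest due within 14 days, and on the repeat samples (weekly, or at whatever frequency the Medical Monitor agrees) for as long as ALT or AST stays above 3x ULN. INR on the retest is the essential part. Carrying it through the repeat samples ensures that any decision to test less often is made with an INR in hand. Extend the post-discontinuation work-up sentence to stops on the INR arm and on the symptom/eosinophilia criterion. The thresholds can stay as they are. If an unseen document already requires INR, a cross-reference in Section 12.2.1 is enough.

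The cost is one extra tube on draws already required, only in patients above 3x ULN, plus wording in Section 12.2.1 and the laboratory manual and the amendment approvals. No visit or endpoint changes. The benefit is bounded: version 10.0 is dated 08 Oct 2021 and the Synopsis estimates completion in December 2022, about 14 months later. Approval time and transitions to commercial ozanimod would shorten that further.
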